### **6.2 Stage 2: Intervention**

After completion of the Baseline Stage, Study RNs will take part in the Intervention which includes protocol training, if needed, and education on the use of B. Braun PA. Note: an RN may join the study in Stage 2 provided they have completed the sites required research training and protocol specific training before participating in Stage 2. Before the Intervention begins, the Study RNs will complete the skill assessment tools to evaluate their confidence and knowledge with respect to catheter insertion. These assessments are located in [Appendix 1: PIVC Insertion Confidence Assessment](#) and [Appendix 2: PIVC Knowledge Assessment](#). The Study RNs will then receive the full training on how to use B. Braun PA Program, which consists of the PA Education Program Curriculum, and in-service on the use of the Christie VeinViewer® Vision2, Introcan Safety® IV Catheters and STEADYCare™ Smallbore Extension Set. The PA Education Curriculum consists of approximately 2 hours of individual, self-paced on-line training and approximately 2 hours of live classroom training and practice.

After completion of the Intervention, the Study RNs will take part in skill assessments of their PIVC therapy confidence and knowledge. These assessments are located in [Appendix 1: PIVC Insertion Confidence Assessment](#) and [Appendix 2: PIVC Knowledge Assessment](#).

This Stage does not include subjects and must be completed before proceeding to the Run-In Stage of the study.

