#### **3.2.1 Registered Nurses**

Only Study RNs from the medical surgical unit(s) or within the ED of the hospital will perform study-related procedures. Registered nurses can be on any shift(s) and will not be required to have a minimum level of clinical experience. Any Study RN who does not complete all of the B. Braun trainings in Stage 2 cannot continue on to Stages 3 and 4 and thus is removed from participation in the study. Years of experience and other demographic information will be collected from the Study RNs in Stage 1 and any RNs who join the study in Stage 2. Study RNs participating in Stage 1 or joining the study in Stage 2 should not be currently using the B. Braun Introcan Safety® IV Catheters and/or the STEADYCare™ Smallbore Extension Set utilized in this study.

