## 12 STATISTICAL ANALYSIS

The statistical evaluation will be performed using the Statistical Analysis Software (SAS®) Version 9.2 or higher (SAS Institute, Cary, NC). All data will be summarized using descriptive statistics, and where necessary, data will also be listed either by subject or by event, as appropriate. For continuous variables, data will be summarized with the number of subjects (N), mean, standard deviation (SD), median, minimum, and maximum. For categorical variables, data will be tabulated with the number and proportion of subjects for each category. Where appropriate, 95% two-sided confidence intervals may be presented. If the observed data are found not to follow a normal distribution, appropriate non-parametric methods may be employed. Two interim analyses are planned.

All hypothesis tests will be two-sided and performed at the alpha=0.05 level. No adjustments to the alpha level will be made for the number of significance tests performed.

Data obtained from all subjects who enroll in any Stage(s) of the study and data obtained from the RN's participating in the study will be included in analysis of safety and the study endpoints.

Additional data driven subgroup analyses may be performed. Additional details on the statistical analyses will be describe in the separate Statistical Analyses Plan (SAP).

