### **12.4 Determination of Sample Size**

Based on initial study design assumptions, at least 316 successful PIVC insertions are necessary to complete Stage 1 and at least 316 successful PICV insertions are necessary to complete Stage 4 in order to detect a statistically significant difference between the current standard-of-care and B. Braun PA at 90% power and two-sided confidence level of 5.0%. The estimated complication rate in Stage 1 is 50% and the estimated complication rate in Stage 4 is 35%. ([Helm, 2015](#))

Two interim analyses are planned, solely for the purpose of sample size re-estimation. Using the method of Pocock & Mehta, the sample size can be either held constant or increased – it cannot be reduced based on the results of the re-estimation.

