#### **Interim Data Analysis Stage 4**

The final sample size in Stage 1 (based on the results of the sample size re-estimation in Stage 1) will be used as the initial sample size for Stage 4. Upon successful completion of approximately 50% of the initial sample size in Stage 4 (which is determined at the interim analysis in Stage 1), another interim analysis on raw (uncleaned) data for the complications will be performed. This sample size re-estimation will follow the method of Mehta and

Pocock to calculate the conditional power of the study to conclude that the complication rate in Stage 4 is lower than the complication rate in Stage 1, given the observed complication rates at the interim analysis. The conditional power (CP) will be categorized into one of the three following zones:

- Favorable:  $CP \geq 90\%$
- Promising:  $41\% \leq CP < 90\%$
- Unfavorable:  $CP < 41\%$

In the event the conditional power is found to be in the Favorable or Unfavorable zone, the study will continue to the originally planned sample size in Stage 4 (i.e., final sample size in Stage 1). In the event the conditional power is in the Promising zone, the total study sample size may be increased to the required sample size to achieve conditional power of 90% at the completion of the study. Note that only the sample size in Stage 4 can be increased at this time, as the data collection in Stage 1 has been completed.

**Registered nurses:** Only RNs from the hospital's ED or medical surgical departments/unit will participate. Registered nurses can be on any shift and will not be required to have a minimum level of clinical experience. There is no minimum number of RNs required.

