### **9.3. Primary Endpoint Analysis**

The primary endpoint analysis will compare the rate/percentage of complications between B. Braun PA in Stage 4 and the hospital's current standard-of-care PIVC in Stage 1. The logistics regression will be used to estimate the differences while controlling the baseline characteristics such as years of nursing experience. Primary efficacy endpoint analysis will be performed at MITT and PP Populations, respectively. If 2 or 3 sites are used, this will be performed individually for each site and across all sites.

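### The nurse pool may change between stages and no analysis models which RN placed each catheter, so operator change cannot be separated from the program and within-nurse correlation is missing from the variance

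*Protocol*

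**What the plan says.** **Who places the catheters.** Any RN on a participating floor or in the ED may become a Study RN for Stage 1 (Protocol 6.1). At Stage 2 the pool can change in two ways: "an RN may join the study in Stage 2 provided they have completed the sites required research training" (Protocol 6.2), and "Any Study RN who does not complete all of the B. Braun trainings in Stage 2 cannot continue on to Stages 3 and 4" (Protocol 3.2.1). SAP 6.1 describes the Stage 4 operators in the same way: Stage 1 nurses and other RNs, provided they completed the program training. On the number of operators, the registered nurses paragraph of Protocol 12.4 says "There is no minimum number of RNs required".

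**How the data are analysed.** Protocol 12.1 compares stages with a binomial test such as Fisher's. The SAP, which prevails where the two differ (Protocol 12.3), has a normal-approximation limit for the rate difference (SAP 6.2) and a model: "The logistics regression will be used to estimate the differences while controlling the baseline characteristics such as years of nursing experience" (SAP 9.3). SAP 9.4 extends that adjustment to the secondary endpoints. SAP 9.2.5 and 9.3 add a stage-by-site interaction and by-site results. None of these contains a nurse effect, a clustered variance or an analysis limited to nurses active in both stages.

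**Current status.** SAP 10 records that the study ended before Stage 2 and that Stage 4 analyses will not be done. Tables for the primary and secondary endpoints are still listed (SAP 14). SAP 9.2.1 permits 95% intervals where appropriate but does not require them.

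**The concern.** The program is delivered through nurses: they are trained, and they use the devices. If less skilled or less motivated nurses drop out at Stage 2, or better ones join, the Stage 4 complication rate can fall without any nurse improving. The SAP synopsis expects about 48 months from study initiation through Stage 4, and each stage must finish before the next starts, so some turnover is likely.

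Years of experience is one trait. It does not measure skill or motivation, nor who leaves and who joins. Confidence and knowledge scores are first taken just before the Stage 2 training, so nurses who never reach Stage 2 have none, and no planned analysis uses them as covariates.

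The second issue is precision. Placements by the same nurse tend to have similar outcomes. A model that treats every placement as independent overstates the information in a single-stage rate. For a difference between stages it misstates the precision, in a direction that depends on how many nurses work in both.

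**Working it through.** **The plan's own figure.** Inputs from Protocol 12.4: 50% against 35%, 90% power, two-sided 5%; "at least 316 successful PIVC insertions are necessary to complete Stage 1", and the same for Stage 4. With pooled variance:

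n = [1.960·√(2·0.425·0.575) + 1.2816·√(0.50·0.50 + 0.35·0.65)]² / 0.15² = (1.370 + 0.886)² / 0.0225 ≈ 227 per stage.

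A continuity correction gives 240 and exact Fisher about 242, so 316 does not follow from the stated inputs. At 316 the power is about 97%. The surplus would absorb a design effect of 316/227 = 1.39, but the documents do not say it was meant for clustering, and extra placements do not correct the error rate or the interval width.

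**Assumptions.** The documents give neither the intraclass correlation (ICC) nor the number of RNs. I take 30 RNs and ICC 0.05 as central values, with ranges of 20 to 40 RNs and 0.02 to 0.10. The only per-nurse volume stated is about 10 insertions in the Run-In (Protocol 6.3), close to 316/30 = 10.5.

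**Single-stage rate.** DE = 1 + (m − 1)·ICC, where m is placements per RN.

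- m = 316/30 = 10.53, so DE = 1 + 9.53·0.05 = 1.48.
- Effective n = 316/1.48 ≈ 214.
- Independent-data half-width at 50%: 1.96·√(0.25/316) = 5.5 points. Clustered: 5.5·√1.48 ≈ 6.7 points.
- Range: 40 RNs with ICC 0.02 gives DE 1.14 and 5.5·√1.14 ≈ 5.9 points; 20 RNs with ICC 0.10 gives DE 2.48 and 5.5·√2.48 ≈ 8.7 points.

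The achieved Stage 1 count is not given. If it were 200 placements from 30 RNs at ICC 0.05, then m = 6.67, DE = 1.28, and ±6.9 becomes ±7.9 points.

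**Stage 4 minus Stage 1.** Let s be the share of placements by RNs working in both stages and r the between-stage correlation of the nurse effect:

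DE = 1 + (m − 1)·ICC − s·m·ICC·r; true one-sided error = 1 − Φ(1.645/√DE).

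With m = 10.53 and ICC 0.05:

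| Shared placements | r | DE | True error of the one-sided 5% test |
|---|---|---|---|
| 0% (or r = 0) | – | 1.48 | 8.8% |
| 50% | 1 | 1.48 − 0.26 = 1.21 | 6.8% |
| 80% | 1 | 1.48 − 0.42 = 1.06 | 5.5% |
| 100% | 1 | 1.48 − 0.53 = 0.95 | 4.6% |

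In the no-overlap case, the ranges of RNs and ICC above give 6.2% to 14.8%. With r = 1, break-even is s = (m − 1)/m, about 0.9. These figures use the one-sided level in SAP 9.2.10. Protocol 12 instead says "All hypothesis tests will be two-sided and performed at the alpha=0.05 level"; at m = 10, ICC 0.05 and no overlap (DE 1.45), the error is 8.6% one-sided and 10.4% two-sided.

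**Operator change, illustration only.** Suppose the program does nothing, but 25% of Stage 4 placements come from joiners whose true rate is 10 points lower. The Stage 4 rate shifts by 0.25·10 = 2.5 points, and the one-sided 5% test at 316 per stage finds in favour of the program 15.5% of the time, even with independent placements.

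**The case against.** **The comparison will not be run.** This stands. No nurse joined at Stage 2 or was removed for incomplete training, so no reported effect is confounded by operator change. SAP 10 does not itself call for a Stage 1 interval; SAP 9.2.1 only allows one. The live consequence is limited to Stage 1 estimates.

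**The SAP does not ignore nurses.** This also stands. A reader might infer that operators are left out altogether, but SAP 9.2.2, 9.3 and 9.4 adjust for experience, the covariate list is open-ended, and by-site analyses are planned. This adjustment addresses neither clustering nor unmeasured skill.

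**Overlap of nurses protects the comparison.** Largely right as to variance. A reader might infer that the stage comparison's limits are necessarily too narrow, or that shared nurses help only if the nurse is in the model. Neither follows. Shared nurses create positive covariance between the two stage rates and so lower the true variance of the difference whatever model is fitted. The plan also expects Stage 1 nurses to continue. Full protection, however, needs about 90% shared placements and fully stable nurse effects, which is demanding for a program meant to change nurse performance.

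**The hypothesis concerns patients' complication rates under the whole program, not change within nurses.** Fair. SAP 6.2 compares complication rates between stages, and the program includes devices as well as training. It would go beyond the documents to make a program claim depend on nurses seen in both stages showing the same direction. That subset is useful supportive evidence, not a success rule.

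**Conclusion.** The point holds as a gap in the design and analysis, with a small practical effect now. The documents allow the operators to change, and nothing planned separates that change from the program. The direction and size of any resulting bias cannot be derived from the documents, and a reader should not infer that bias has occurred.

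On precision, a Stage 1 interval that treats placements as independent is too narrow for any positive within-nurse correlation. It should be about ±6.7 instead of ±5.5 points under 316 placements, 30 RNs and ICC 0.05, all of them assumed. For the dropped stage comparison, at the same ICC and per-nurse volume, the one-sided 5% test would have had between about 8.8% error (no shared RNs or uncorrelated nurse effects) and slightly below nominal (full overlap, stable effects).

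**What to change.** **Now, in SAP 9.3 and 9.4.**

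- Link each placement to a coded RN identifier. The experience covariate already needs this link, and the assessment forms in Protocol Appendices 1 and 2 carry an RN identification field. The per-placement eCRF items listed in Protocol 6.1 and 6.4 do not name the inserting RN, so confirm that the database holds it. A coded identifier is compatible with the clinician-identity rule in Protocol 13.6.
- Use RN-clustered standard errors or an RN random effect.
- Use the clustered interval for any Stage 1 rate that is reported, and state how many RNs contributed.

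**If the design is restarted or reused.** Keep the same model for the stage comparison, add a supportive (not decisive) analysis limited to RNs with placements in both stages, report how many RNs left and joined, and state an assumed ICC in the sample size section.

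**Cost.** SAP wording and a little programming, with no new data if the link exists. Intervals will usually be somewhat wider, and the both-stage analysis will use fewer placements.

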### **6.3 Stage 3: Run-In**

Only Study RNs that completed Stage 2 will participate in this Stage. After the successful completion of the Intervention, it is expected that all current PIVC catheters and extension sets will be collected from the department(s)/unit(s) and only B. Braun PA products will be available. If this cannot be accomplished, the Investigator or designee will take reasonable

measures to ensure that all Study RNs use only B. Braun and Christie Medical study products on their patients.

This Stage will last approximately 3 weeks in order for the Study RNs to become familiar with the B. Braun devices in a clinical setting. It is anticipated that each Study RN will perform approximately 10 insertions during this 3 week time period ([Reznek, 2002](#)).

These Study RNs will use the B. Braun devices for all their patients requiring PIVC from this point forward. There is no minimum number of patients required to complete this Stage, and clinical data on these patients will not be collected.

#### **6.4 Stage 4: Post-Interventional**

Only Study RNs will participate in this Stage. Upon completion of the Run-In Stage, the Post-Interventional Stage will begin. At least 316 successful PIVC placements are required in this Stage. Study subjects or their LAR will be consented by Study RNs and must meet all inclusion and none of the exclusion criteria prior to any study related procedures. The Study RNs should use the B. Braun devices for all of their PIVC study subjects. Study RNs will use their standard procedures and supplies for PIVC dressing. The catheter insertion site, characteristics, number of attempts, dressing condition, complications and removal information (length of indwell time in hours and reason for removal) will be recorded in the eCRF for each attempt. The subject's demographic data (age, gender) will be collected. The catheter and site of insertion will be examined daily and any relevant clinical findings will be recorded in the eCRF. At the time of catheter removal the reason for removal of the catheter will be documented. If the attempts fail and the subject requires a different catheter, such a PICC, Midline or Central Catheter, or a PIVC from a different manufacturer will be recorded in the eCRF.

After completion of the study, the Study RNs will re-take the skill assessments of their confidence and knowledge with respect to B. Braun PA. These assessments are located in [Appendix 1: PIVC Insertion Confidence Assessment](#) and [Appendix 2: PIVC Knowledge Assessment](#).

A summary of the study Stage name, Stage number, number of subjects/patients and product training used or Intervention is displayed in [Table 1](#).

**Table 1: Summary of Stage name, Stage number, number of subjects and product used or Intervention**

Stage Identification	# Subjects/Duration	Product/Intervention
Baseline (Stage 1)	316 successful PIVC placements	Hospital PIVC Standard-of-Care
Intervention (Stage 2, Education)	RNs only/ training a	B. Braun Peripheral Advantage Education Curriculum a + product training
Run-In (Stage 3)	~ 3 weeks	B. Braun Supplies b
Post-Interventional (Stage 4)	316 successful PIVC placements	B. Braun Peripheral Advantage Supplies b

a B. Braun Peripheral Advantage Education Curriculum = Approximately 2 hours of self-paced on-line training followed by approximately 2 hours live/hands on class room training on the use of the PA products

b B. Braun Peripheral Advantage supplies = Christie VeinViewer® Vision2, Introcan Safety® IV Catheters, and

---

STEADYCare™ Smallbore Extension Set

## 7 SKILL PERFORMANCE ASSESSMENTS

The Study RNs will take skill/performance assessments (PIVC Insertion Confidence Assessment and PIVC Knowledge Assessment) before and after completion of the RN Intervention and again after the completion of the Post-Interventional Stage. The skill/performance assessments (PIVC Insertion Confidence Assessment and PIVC Knowledge Assessment) are presented in [Appendix 1: PIVC Insertion Confidence Assessment](#) and [Appendix 2: PIVC Knowledge Assessment](#).

## 8 DEVICE REMOVAL

It is expected that the Study RNs will evaluate the catheter site before the catheter is removed. Once the catheter is removed by the Study RN, Standard facility protocols will be followed for catheter removal and the dressing of the IV site. The dressing of the IV site may be performed by a non-study nurse, however the date and time of removal and the reason for removal must be recorded.

A catheter may be removed at the end of a subject's medical treatment, as a result of complications or for any other reason determined by the treating clinician. If PIVC therapy is still required after catheter removal, the subject may continue to receive PIVCs in accordance with his/her treating physician. If the PIVC was removed as a result of complications, the subject may not continue in or re-enter the study and will be considered a Study Completer. Complications will be assessed as potential Adverse Events (AEs) as described in [Section 11](#). If the PIVC was removed as a result of treatment completion (i.e., subject no longer requires a PIVC) he/she will be considered a Study Completer. In addition, if he/she was subsequently discharged from the facility, then he/she may re-enter the study in the same or different Stage if a re-admission for any reason is required.

The Study RN or designee will record in the eCRF if the PIVC was removed at any time due to any of the following complications: phlebitis/thrombophlebitis, occlusion, infection (localized or Catheter Related Bloodstream Infection [CRBSI]), dislodgement or infiltration, extravasation, or accidental removal. If it is medically appropriate for the subject, the PIVC may also be removed due to other conditions(s). The subject may continue to receive PIVC catheters in accordance with his/her medical treatment. If the PIVC was removed for a complication, then the subject may not continue or re-enter into the study and he/she is considered a Study Completer. Complications will be assessed as potential AEs as described in [Section 11](#).

If the PIVC was removed as a result of treatment completion (i.e., subject no longer requires a PIVC) he/she will be considered a Study Completer. In addition, if he/she was subsequently discharged from the facility, then he/she may re-enter the study in the same or different Stage if a re-admission for any reason is required.

## **9 PROTOCOL INCIDENTS/DEVIATIONS**

Procedures and forms for reporting clinical study incidents and deviations will be reviewed during the site initiation prior to study execution. All incidents and deviations will be recorded in the eCRF.

### **9.1 Incidents**

A Study Incident is defined as any problem involving any of the study devices, reference methods, procedures, equipment, and human subjects as a result of execution of this protocol. Study Incidents may adversely (or potentially adversely) affect human safety, the integrity of the evaluation data, and/or the operation of devices or systems. Any incident which affects the health, safety, and welfare of human subjects will be reported as an Adverse Event (AE) (See [Section 11](#)). In the event an Incident results in an injury to a Study RN, the incident will be evaluated by the Investigator to determine the severity (mild, moderate, severe) and relationship to B. Braun PA (none, unlikely, possible, probable, or definite).

Examples of Study Incidents that are not AEs may be mislabeling or adulteration of the investigational device, device malfunctions that do not contribute to or cause an AE, or damage to devices caused by shipping or handling. Device malfunctions are defined as failure of an investigational medical device to perform in accordance with its intended purpose when used in accordance with the instructions for use or clinical investigational protocol. Incidents resulting in an AE or protocol deviation will be documented in the EDC.

